2.1 Study design

The SAFIR-TOR trial is a prospective biomarker study that aims to show that p4EBP1 staining predicts clinical benefit from treatment with the mTOR inhibitor everolimus in patients with locally advanced or metastatic breast adenocarcinoma which cannot be treated with surgery and/or radiation therapy.

2.1.1 Planned study duration

- A 36-month period of accrual is planned for a sample size of 150 patients.
- The expected treatment duration with the combination everolimus (EVE) and exemestane (EXE) is 10 months.
- Post-treatment duration follow-up period: 36 months.
- Estimated duration of the study: 64 months.

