2.2 Study endpoints

2.2.1 Primary endpoint

The primary endpoint of the trial is the predictive value of p4EBP1 in determining mTOR inhibitor efficacy, measured by the association between expression level of the biomarker (high vs low expression) and clinical benefit rate (CBR) 6 months after initiating EVE-EXE treatment. Clinical benefit at 6 months is defined as a complete or partial response or stable disease at 6 months after treatment initiation.

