4.1.3 Study treatment administration

The following data will be summarized for each treatment (exemestane and everolimus):

- Number of patients who received at least one dose of treatment
- Treatment duration
- Dose received at treatment initiation
- Number of patients with at least one dose modification (Yes/No) and reason
- Number of patients with definitive discontinuation of study treatment (Yes/No) and reason

Note that the end of treatment is defined as the date at which everolimus was discontinued (for whatever reason), or when a new antineoplastic treatment is initiated. A definitive discontinuation of exemestane is not considered as a discontinuation of study treatment.

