4.2.2 Secondary endpoints

- **Progression-free survival (PFS)** will be measured from the date of treatment initiation to the date of event defined as the first documented disease progression or death from any cause. Patients with no event at the time of analysis will be censored at the date of last adequate tumor assessment. The date of first progression will be determined using data from the tumor evaluation form.
- **Overall survival (OS)** will be measured from the date of treatment initiation to the date of death from any cause. Patients who are alive at the time of analysis will be censored at the date of last contact. Number of patients deceased and cause of death will be reported.

PFS and OS will be estimated using the Kaplan-Meier method. Survival curves will be plotting according to p4EBP1 (high vs low) and compared using a logrank test.

A Cox proportional hazards model will be performed to explain the progression-free survival time. Variables sufficiently informed (less than 10% missing values) and significant at a 15% level in a univariate approach will be included in a backward selection procedure to keep factors significant at a 5% level in the final multivariate model. Hazard ratios (HRs) will be presented with their 95% confidence intervals (CI).

- The clinical benefit rate at 6 months will be described with its 95% confidence interval according to:
 - the presence/absence of each studied genomic event
 - the expression levels of each studied proteomic biomarker (cutoff will be defined in the same way as mentioned for the primary endpoint)
- Descriptive statistics will be used to **characterize the molecular landscape** of endocrine-resistant disease in terms of genomic events observed. Correlations between the different types of genomic events will be studied.

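### Does the stated study duration of 64 months contradict the accrual, treatment and follow-up periods listed beside it?

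*SAP*

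**What the plan says.** Section 2.1.1 of the SAP, part of the introduction, gives four planning figures:

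- Accrual: "A 36-month period of accrual is planned for a sample size of 150 patients".
- Treatment: "The expected treatment duration with the combination everolimus (EVE) and exemestane (EXE) is 10 months".
- Follow-up: "Post-treatment duration follow-up period: 36 months".
- Total: "Estimated duration of the study: 64 months".

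It does not say whether the 36 months of follow-up is a minimum, an average or a maximum, and it names no closing date. Section 2.1.2 covers only early termination. Section 4.1.3 fixes when treatment ends ("Note that the end of treatment is defined as the date at which" everolimus stops, or a new antineoplastic treatment starts), so post-treatment time has a defined origin. For OS, section 4.2.2 states: "Patients who are alive at the time of analysis will be censored at the date of last contact". That time of analysis is not dated.

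**The concern.** A reader who lays the three periods end to end for the last patient enrolled expects a study well beyond 64 months. The shortfall is too large to be rounding. It does not hinge on the treatment estimate either, because accrual and follow-up alone already exceed the total.

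At stake would be the observation time of late entrants. These are the SAP's only figures for planned follow-up. If month 64 closed the study, the last patient would have half the listed post-treatment follow-up, and OS would be less mature in the later half of the cohort. A reader could not tell from the SAP which follow-up was meant.

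**Working it through.** **Inputs** (SAP section 2.1.1): accrual 36 months, expected treatment 10, post-treatment follow-up 36, stated total 64. I assume that treatment starts at entry and lasts the expected 10 months. All follow-up times below are potential follow-up, before any death or withdrawal.

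**Plain sums against 64**

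| Components | Sum (months) | Difference from 64 |
|---|---|---|
| Accrual + treatment + follow-up | 36 + 10 + 36 = 82 | +18 |
| Accrual + follow-up | 36 + 36 = 72 | +8 |
| Accrual + treatment | 36 + 10 = 46 | −18 |
| Treatment + follow-up | 10 + 36 = 46 | −18 |

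No plain sum gives 64. A full 36 post-treatment months for the last patient by month 64 would need 64 − 36 − 36 = −8 months of treatment. A guaranteed 36 months for everyone is therefore incompatible with 64.

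**Reading 1: 36 months is an average.** With even accrual over 36 months, the mean entry time is 36/2 = 18 months. With a common close:

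- total = mean entry + treatment + mean follow-up = 18 + 10 + 36 = 64, the stated figure;
- first patient: 64 − 0 − 10 = 54 post-treatment months;
- last patient: 64 − 36 − 10 = 18 post-treatment months.

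The 18-month gap is exactly half the accrual period, which is what this reading predicts.

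**Reading 2: 36 months is a maximum, cut at month 64.** The full 36 months is reached by patients entering up to month 64 − 10 − 36 = 18. Later entrants have less, down to 18 months for the last. The four figures stand here too.

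**What depends on the total**

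- *Primary endpoint.* It is fixed in time from the start of treatment: "Clinical benefit at 6 months is defined as a complete or partial response or stable disease at 6 months after treatment initiation". Section 4.2.1 uses a window up to 7 months, so the last patient's window closes at about 36 + 7 = 43 months, which is 64 − 43 = 21 months before the stated end.
- *Sample size and power* (section 3.1). These rest on 120 evaluable patients, the two benefit rates and the test level. Study length does not enter.
- *PFS and OS* (section 4.2.2). Patients without an event are censored at the last adequate tumour assessment (PFS) or last contact (OS). Kaplan-Meier, logrank and Cox methods allow for unequal follow-up. No event target, power or minimum follow-up is set for either.
- *OS time for the last patient.* Measured from the start of treatment, potential follow-up is 64 − 36 = 28 months if the study closes at 64, and 10 + 36 = 46 months if it runs to 82. The difference is 18 months, in how much late OS information exists.

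**The case for a change.** The strongest case for a change is that the SAP itself prints four figures that do not add up on their most natural reading, so the point is more than detail left to the protocol. An estimate should follow from its listed components, and an 18-month difference is 28% of the stated total (18/64). The survival analyses have no dated cut-off, and one added sentence would settle the matter.

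Part of this stands. The arithmetic is right, the basis of the 36 months is not given, and the average reading is an inference from the numbers that the SAP does not state. A minimum of 36 months for everyone cannot be squared with 64.

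The rest does not carry. The SAP never promises each patient 36 months, so the figures need not conflict, and nothing shows that any one of them is wrong. The closing date and follow-up schedule normally sit in the protocol, which is not at hand. The cheap remedy would reword background text and leave every definition, population and test as it is.

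**Conclusion.** No change to the plan follows. The mismatch is real on a plain sum (82 against 64 months, or 72 with no treatment time). It disappears if 36 months is an average under even accrual with a common close (exactly 64, range 18 to 54 months), or a maximum cut at month 64. Both readings assume treatment starts at entry and lasts the expected 10 months; the SAP states neither.

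Even if one of the figures is a slip, the specified results are unaffected: the primary endpoint is complete near month 43, and nothing in the sample size or the analyses uses the 64 months. The most that turns on it is 18 months of potential OS follow-up for the last entrant, in a secondary analysis whose method already handles unequal follow-up. This is an unexplained planning figure, to be clarified if section 2.1.1 is edited for another reason.

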2.1.2 Trial early termination criteria

The trial can be suspended or stopped by the sponsor in agreement with the coordinating investigator and the Steering Committee and/or the competent authority and/or the ethics committee (EC) for the following reasons:

- Unexpected occurrence or severity of toxicity linked to the biopsy procedure.
- Insufficient patient recruitment.
- Poor quality of data collection.

Figure 1. Study design

2.2 Study endpoints

2.2.1 Primary endpoint

The primary endpoint of the trial is the predictive value of p4EBP1 in determining mTOR inhibitor efficacy, measured by the association between expression level of the biomarker (high vs low expression) and clinical benefit rate (CBR) 6 months after initiating EVE-EXE treatment. Clinical benefit at 6 months is defined as a complete or partial response or stable disease at 6 months after treatment initiation.

2.2.2 Secondary endpoints

- Predictive value of genomic events in determining mTOR inhibitor efficacy where genomic events are defined as mutations, amplifications, gains, and losses.
- Predictive value of protein biomarkers (pTEN, AKT, pSRB, LKB1) in determining mTOR inhibitor efficacy.
- Molecular landscape of endocrine-resistant disease, in particular correlations between genomic events observed

3 General statistical methods and analysis population definition

3.1 Sample size

The primary endpoint of the study is the association between expression levels of p4EBP1 (high vs low expression) and clinical benefit after 6 months of EVE-EXE treatment (CBR-6m).

We plan to enroll 150 patients in the study in order to have a minimum of 120 patients evaluable for the primary endpoint (some patients may not be evaluable: their tumor samples may not being analyzable, patients may not have been treated with the treatment combination [EVE-EXE]...).

With a sample size of 120 patients (60 patients in each subgroup defined by low vs high expression), a twogroup chi-square test with a 0.05 two-sided significance level will have 80% power to detect an increase in CBR at 6 months corresponding to an odds ratio of 2.8 (from 30-40% in p4EBP1- group to 55-65% in p4EBP1+ group). We estimate that this benefit, compared with those observed in the TAMRAD study (Bachelot, 2012), will reflect a clinically meaningful predictive value of the studied biomarker.

3.2 General statistical methods

Quantitative data will be described using the number of observations, mean, standard deviation, median, minimum and maximum values.

Qualitative variables will be described using frequency and percentage distributions. The number of missing data will be given, but will not be considered for the calculation of proportions.

All confidence intervals and statistical tests will be 2-sided and performed at a 5% level. P-values \geq 0.001 will be reported to 3 decimal places; p-values less than 0.001 will be reported as "<0.001".

Statistical analyses will be performed using SAS® software version 9.4.

3.3 Analysis population definition

Global population: all patients included.

Efficacy analysis population: A patient will be considered evaluable if:

1) no major violation of eligibility criteria, 2) the patient has received at least one dose of everolimus, 3) the patient has at least one tumor evaluation performed before and another 6 months after treatment initiation and 4) an expression levels of p4EBP1 is available for the patient.

Safety population: all patients having received at least one administration of treatment, either everolimus or exemestane.

4 Statistical Analysis

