4.2 Efficacy endpoint

4.2.1 Primary endpoint

For the primary endpoint, the analysis will be performed on the efficacy population and will include all treated and evaluable patients. A patient will be considered as evaluable if 1) no major violation of eligibility criteria, 2) the patient has received at least one dose of everolimus, 3) the patient has at least one tumor evaluation performed before and another 6 months after treatment initiation and 4) an expression levels of p4EBP1 is available for the patient. The clinical benefit rate at 6 months (CBR-6m) will be defined as the proportion of patients with a complete response, a partial response, or a stable disease 6 months after initiation of treatment. The CBR-6m and its associated 95% confidence interval (CI) will be described globally and according to high vs low p4EBP1 expression, and will be compared between the 2 subgroups using a chi-square test. In the absence of assumptions, the choice of cut-off for dichotomized the population depending on p4EBP1 values will be done using the median value of the biomarker distribution, the aim being to consolidate data into subgroups of comparable strengths to maximize the power. A second cut-off will be determined using the X-tile software, proposing a division of the population for an optimal separation of data seeing the responses. This second analysis will be considered as a sensitivity analysis.

Logistic regression analyses will be performed to assess the predictive potential effect of biomarker level on clinical benefit rate at 6 months (Yes/No). Clinical factors known to be predictive of clinical benefit will be added to the model to verify the independence of the marker. A step-by-step descending selection of variables will be used to retain factors that were independently linked to clinical benefit. All variables sufficiently informed (with <10% missing value) and significant (at 15% level) in the univariate approach will be introduced in the initial multivariate model. The final multivariate model will be include only variables which will be statistically significant at a 5% threshold. Odd ratio (OR) will be presented with 95% confidence interval (CI). A p-value <0.05 will be considered statistically significant.

For each patient, the variable "clinical benefit rate at 6 months Yes/No" will be determined as follows:

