- (1) if a progression is recorded in the tumor evaluation form and if the duration between treatment initiation (everolimus) and the first documented progression is ≤7 months, then the variable "clinical benefit rate at 6 months" will be set to "no"
- (2) if condition (1) is not fulfilled and a complete response, a partial response or a stable disease is recorded in the tumor evaluation form, and if the duration between treatment initiation (everolimus) and the tumor evaluation form is ≥5 months, then the variable "clinical benefit rate at 6 months" will be set to "yes"
- (3) if condition (2) is not fulfilled and if we have no tumor evaluation between 5 and 7 months after treatment initiation and patient is non progressive or without tumor evaluation before 5 months but progressive after 7 months, or non-progressive in last evaluation occurring within 5 months then the primary endpoint "clinical benefit rate at 6 months" will be defined patient by patient during blind review but blinded to p4EBP1 level.
- (4) if condition (3) is not fulfilled and if the patient died before 7 months from other cause than clinical progression, then the variable "clinical benefit rate at 6 months" will be set to "Not Available".

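### The efficacy set requires a 6-month tumor evaluation with no exception for earlier progression, which contradicts outcome rule (3) and, by implication, rule (1)

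*SAP*

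**What the plan says.** Section 3.3 lists four conditions for the efficacy population. The third is that "the patient has at least one tumor evaluation performed before and another 6 months after treatment initiation". Section 4.2.1 restricts the primary analysis to this population and repeats the condition in the same words: "3) the patient has at least one tumor evaluation performed before and another 6 months after treatment initiation". Neither place adds an exception for earlier progression.

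Section 4.2.1 then derives the yes/no outcome, beginning "For each patient, the variable". Two of its rules matter here:

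- Rule (1) gives 'no' "if a progression is recorded in the tumor evaluation form and if the duration between treatment initiation (everolimus) and the first documented progression" is at most 7 months. It sets no lower time limit and does not ask for an evaluation near 6 months.
- Rule (3) leaves the outcome to a patient-by-patient review, blinded to p4EBP1, for cases that include those "if we have no tumor evaluation between 5 and 7 months after treatment initiation" and those "non-progressive in last evaluation occurring within 5 months".

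Section 3.1 plans 150 enrolled patients to obtain at least 120 evaluable for the primary endpoint.

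**The concern.** The primary endpoint is clinical benefit at 6 months, and early progression is an obvious way to fail it. A patient who progresses early may well have no further tumor evaluation at 6 months. If such an evaluation is a condition for being counted, membership of the analysis set depends on the outcome: those with benefit stay in, and part of those without benefit drop out.

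Two programmers working from this SAP could therefore produce different denominators and different CBR-6m. Because the high/low cut-off is the median of the biomarker distribution, they might also obtain different p4EBP1 groups. The SAP does not say which text prevails, and that choice should not be left until outcomes are known.

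**Working it through.** **1. The texts side by side**

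| Patient | Criterion 3, read literally | Outcome rule in 4.2.1 |
|---|---|---|
| Last evaluation at 4 months, no progression | Not evaluable | Rule (3): blind review |
| Progression recorded at 2 months, no later evaluation | Not evaluable | Rule (1): 'no' |
| Progression recorded at 6 months | Evaluable | Rule (1): 'no' |
| No evaluation before 5 months, progression first found after 7 months | Not clearly excluded; an evaluation later than 6 months exists | Rule (3): blind review |

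The first row is an explicit contradiction, because rule (3) names a group that criterion 3 shuts out. The second is a conflict by implication, since rule (1) also covers progressors who do have an evaluation near 6 months. The last two rows raise no clear conflict.

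**2. The plan's own figure**

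Inputs from section 3.1: 60 patients per group, two-sided 0.05, CBR from 30-40% to 55-65%, odds ratio 2.8, power 80%.

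Power = Φ[(p₂ − p₁ − 1.96·s₀)/s₁], with s₀ = √[p̄(1 − p̄)(1/n₁ + 1/n₂)] and s₁ = √[p₁(1 − p₁)/n₁ + p₂(1 − p₂)/n₂].

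For 30% vs 55%: s₀ = 0.0903, s₁ = 0.0873, and power = Φ(0.837) = 79.9%. For 40% vs 65%: 79.0%. The stated 80% reproduces and is not in dispute.

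**3. Effect of the literal criterion on CBR-6m**

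The share L of failures without a 6-month evaluation is not in the SAP. I assume 10%, 25% and 50%, equal in both groups, with group membership held fixed. All successes and (1 − L) of the failures are kept, so CBR becomes p/[p + (1 − p)(1 − L)].

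Example, L = 25%: 0.30/(0.30 + 0.70 × 0.75) = 0.364 and 0.55/(0.55 + 0.45 × 0.75) = 0.620.

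| L | 30% vs 55% becomes | 40% vs 65% becomes |
|---|---|---|
| 10% | 32% vs 58% | 43% vs 67% |
| 25% | 36% vs 62% | 47% vs 71% |
| 50% | 46% vs 71% | 57% vs 79% |

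**4. Effect on the odds ratio**

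The odds ratio is multiplied by (share of failures kept, low group)/(share kept, high group). Equal shares leave it unchanged. For 30% vs 55% it is (0.55/0.45)/(0.30/0.70) = 2.85. Keeping 50% of failures in the low group and 60% in the high group (assumed) gives 2.85 × 0.5/0.6 = 2.38; the reverse gives 3.42.

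**5. Effect on power**

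This depends on whether the 120 counts patients before or after criterion 3.

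| L | Power, losses taken from 120 (30/55; 40/65) | Power, 60 per group retained (30/55; 40/65) |
|---|---|---|
| 10% | 78%; 77% | 80%; 79% |
| 25% | 74%; 72% | 81%; 78% |
| 50% | 65%; 61% | 80%; 72% |

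In the first column N falls to about 113, 103 and 86 (30/55) or 114, 106 and 92 (40/65). The number needed before exclusion to retain 120 is 120 × 120/N. For 30/55 at 25% this is 120 × 120/102.75 = 140, within the 150 only if other losses stay at about 10. At 50% it is 120 × 120/85.5 = 168, which exceeds 150.

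**The case against.** The strongest reply is that a derivation rule may cover more patients than the analysis set. Section 4.2.1 derives a variable for each patient, and the population definition then chooses who is analyzed. On that view rule (1) does not contradict criterion 3. This stands in part, and it is why the conflict with rule (1) is put as an implication only. It does not rescue rule (3): a blind review of patients last seen without progression within 5 months serves no purpose for the primary endpoint if none of them can be analyzed.

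The criterion may also have been meant as an evaluation within 6 months of starting treatment. That would ease the conflict, but the text does not say so in either place.

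A reader might infer that the trial is underpowered, with power as low as 61-65%. The SAP does not support this. Section 3.1 already calls the 120 evaluable, criterion 3 is part of that definition, and 30 of the 150 patients are allowed for losses. Subtracting again from 120 may count the same loss twice.

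A reader might also infer from section 3.1 that early progressors were meant to be kept, because its examples of non-evaluability are that "their tumor samples may not being analyzable, patients may not have been treated with the treatment combination" was not possible. That list is open-ended, and the section does not say which set its planning rates describe, so neither settles the matter.

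**Conclusion.** The SAP is inconsistent as written about who is in the primary analysis. Criterion 3 contradicts rule (3) explicitly and rule (1) by implication. Applied literally, it removes mainly failures and inflates CBR-6m in both groups, by 6 to 7 percentage points at the planning rates if a quarter of failures lack a 6-month evaluation. That share is an assumption, and a median cut-off recomputed on the reduced set would shift the figures.

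The comparison between p4EBP1 groups is biased only if the share lost differs between them. The SAP gives no evidence either way. A power loss follows only if more patients are lost than the 150-to-120 allowance covers, which cannot be determined from the document. If the analysts already follow rule (1), early progressors are counted as failures and only the text is at fault. The point should be fixed, but it does not show that the planned sample size or test is wrong.

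**What to change.** In 3.3 and 4.2.1, replace criterion 3 by: *a baseline tumor evaluation and at least one post-baseline tumor evaluation*. Progressions recorded on the tumor evaluation form at up to 7 months then stay in the set as 'no' under rule (1), and patients without an evaluation between 5 and 7 months can reach blind review under rule (3).

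No further clause admitting documented progression is needed. Rule (1) scores only progression recorded on the form, so such a clause would be redundant or would admit patients whom rule (1) cannot score.

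The cost is one phrase in two places, with no new data. The reported CBR-6m will be lower than under the literal criterion, and some more patients may go to the blind review already planned. Nothing changes for early progressors if the analysts already follow rule (1).
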